9. STATISTICAL METHODS AND SAMPLE SIZE DETERMINATION

NeoRad is a multicenter, open, randomized phase III study aiming to estimate the efficacy of changing the sequence of surgery and radiotherapy in high-risk breast cancer by comparing DFS as the primary endpoint and secondary endpoints between the treatment arms.

9.1 Randomization and stratification

Patients will be randomized to either the experimental arm or the standard of care arm in a 1:1 ratio, stratified by the following parameters:

- 1) biological subtype: Strata: Her2-type (HER2/neu positive), HR + type (no HER2/neu overexpression), triple negative
- 2) cN-Status (before start of NACT): Strata: cN+, cN-

- type of planned surgery: Strata: type of planned surgery: Strata: BCS vs Mastectomy (NSM, SSM or radical)

9.2 Description of analysis sets

9.2.1. Efficacy analysis set

The full analysis set or ITT (intention to treat or “treatment policy”) set will be the primary population for efficacy endpoints, notably for the primary endpoint DFS. For the ITT analysis, all randomized patients will be included as randomized, regardless of possible errors after randomisation.

Patients who have received protocol treatment unless they experience unequivocally documented earlier disease progression and have no major protocol deviations thought to impact the efficacy conclusions of the trial will be included in the per protocol set for the sensitivity analysis of non-inferiority; the final list of the major protocol violations leading to

the exclusion from the per protocol set will be defined in the statistical analysis plan (SAP); patients who were enrolled although they unequivocally did not fulfil the selection criteria of the trial a priori (“non-eligible”) will be excluded from the per protocol set.

9.2.2 Safety analysis set

All patients who have received breast surgery or at least one fraction of radiotherapy will be included in the safety analysis set. For this analysis, patients will be grouped according to the treatment they actually received, accounting for errors after randomization; patients who only received surgery and no radiotherapy will be included together with the post-surgery radiotherapy.

Toxicity, quality of life endpoints as well as the cosmetic results will be analysed based on the safety set.

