3. STUDY OBJECTIVES

3.1 Primary objective

Primary objective is the superiority of PRT of the experimental treatment schedule in terms of disease-free survival (DFS)* compared to the standard arm. We will perform a hierarchical test, starting with non-inferiority as the first primary analysis. If this is significant, then testing superiority as the second component of the main analysis will be performed.

If only non-inferiority but not superiority is confirmed, the cosmetic results (key secondary endpoint) need to be better in the preoperative radiotherapy arm for the study to be able to change clinical practice.

The investigated PRT-schedule consists of 5x 2.7 Gy per week to 40.5 Gy Standard-RT** prior to surgery. In case of planned breast-conserving surgery, a boost has to be administered in case of residual tumor after NACT. The boost can be administered percutaneously as simultaneous integrated boost (5x per week additional 0.5 Gy to 48 G) or after whole breast irradiation (3x 3.5 Gy to 10.5 Gy) or as an intraoperative boost. Intraoperative radiotherapy is administered with 10 Gy electrons of adequate energy.

**Standard RT is defined as radiotherapy of the breast +/- boost +/- lymph node regions.

*DFS is defined as the time in months between the breast cancer diagnosis and the disease recurrence (local or regional recurrence, contralateral breast cancer, distant metastases, second invasive cancer or death of any cause).

Table 1: Definition of disease-free survival

Event	DFS	Time from randomisation until
Locoregional recurrence	E	Date of locoregional recurrence
Lymph node recurrence	E	Date of lymph node recurrence (in the ipsilateral axillary, supra-/infraclavicular (including Rotter), and internal mammary chain lymph nodes)
Contralateral breast cancer	E	Date of contralateral breast cancer
Any distant metastatic disease	E	Date of distant metastases
Invasive non-breast cancer	E	Date of invasive non-breast cancer diagnosis
Treatment-related death	E	Date of death
Death of breast cancer	E	Date of death
Death of other cancer	E	Date of death
Non-cancer related death	E	Date of death
Death of unknown cause	E	Date of death
Under observation without event or lost to follow-up	C	Date last follow-up

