3.2 Secondary objectives

Assessment and comparison between randomized arms of

- 1) time to local recurrence [in affected breast] (LR) as a first site of recurrence: recurrence in affected breast counts as an event; regional recurrence, distant recurrence, contralateral breast cancer, invasive non-breast cancer, death due to any cause are considered competing risks.
- 2) time to regional recurrence (RR) as a first site of recurrence: recurrence in the regional lymph nodes counts as an event, local recurrence, distant recurrence, contralateral breast cancer, invasive non-breast cancer, death due to any cause are considered competing risks.
- 3) distant disease-free survival (DDFS): distant recurrence, invasive non-breast cancer and death due to any cause are considered as events.
- overall survival (OS): death due to any cause is considered as an event.
- 5) breast cancer specific survival (BCSS): death due to breast cancer is considered as an event; in case of unknown death cause all effort will be made to determine the cause; if at the time of analysis there are still any deaths due to the unknown reason, they will be counted as tumor-related (worst case principle).

Time for all time-to-event endpoints will be computed starting from randomization after end of NACT.

- 6) pathological complete remission (pCR, defined as ypT0/is ypN0) rates.
- 7) cosmetic results (5 Point Scoring System, key secondary objective and subjective
- 8) breast retraction assessment=BRA)
- 9) quality of life (EORTC C30 and EORTC QLQ-BR23)
- 10) rate of arm lymph edema >°I of the irradiated side
- 11) plexopathy >°I of brachial plexus of the irradiated side

12) acute (up to 3 months after the end of radiotherapy) and late (after 3 months) toxicity (CTC 5.0, LENT-SOMA)

Definitions of outcome measures (clinical Trials.gov):

1. local recurrence rate [in affected breast] (LR) [Time Frame: 6 to 10 years]
Rate of cancer that has recurred at the same location as the primary cancer. This is a way to measure how well the new treatment is working.
2. locoregional recurrence rate (LRR) [Time Frame: 6 to 10 years]
Rate of new cancer at any locations (regional lymph nodes, chest wall/mastectomy site) on side which was previously affected by the primary cancer.
This is a way to measure how well the new treatment is working.
3. disease metastases free survival (DMFS) [Time Frame: 6 to 10 years]

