Regarding the primary endpoint the following predefined subgroups will be analysed in the similar way (stratified by the remaining stratification factors in case of a subgroup defined by a stratification factor): subgroups by biological subtype (HER2+ vs HER2-negative/HR-positive vs TNBC); ME, BET, Implant+/- Mesh. An interaction test will be performed for treatment against biological subtype. No adjustment for multiplicity is planned, the results should be considered as exploratory.

All secondary endpoints are defined in section 3.2.

The following secondary time-to-event endpoints will be analysed in a similar way (except for the non-inferiority): DDFS, OS, DSS.

LR (as a first site of recurrence) and RR (as a first site of recurrence) will be analysed using competing risk models: cumulative incidence function will be plotted and compared between treatment arms using (stratified) Gray's test; 5 year and 8-year cumulative incidence rates will be reported with the respective 95% CI; multivariate Fine-Gray model including treatment and stratification will be used to estimate hazard ratios with 95% CI.

Rates will be reported with 95% CI. Comparisons of the categorical data will be performed using Fisher's exact test (for pCR rates), or a trend test according to Cochran/Armitage (e.g. for cosmetic results), as suitable; further explorative multivariate analyses, including other relevant models (e.g. logistic regression) will be performed if deemed useful. Subgroups analyses in the same predefined subgroups as for the primary analysis will be performed if deemed useful.

If only non-inferiority but not superiority is confirmed, the cosmetic results (dichotomized as excellent/good vs moderate or worse, key secondary endpoint) must be better in the preoperative radiotherapy arm for the study to be able to change clinical practice. With the sample size of the study, the exact test of Fisher will have over 90% power to detect a clinically relevant improvement by 15% irrespective of the rate of excellent/good cosmetic results in the control arm.

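### Section 9.2.2 groups the key secondary cosmetic endpoint by treatment received, although its objective compares randomised arms and a practice change can rest on it

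*Protocol*

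**What the plan says.** Section 9.2.2 defines the safety set as patients who had breast surgery or at least one fraction of radiotherapy. In it, "patients will be grouped according to the treatment they actually received", and "patients who only received surgery and no radiotherapy will be included together with the post-surgery radiotherapy". It then assigns endpoints to the set: "Toxicity, quality of life endpoints as well as the cosmetic results will be analysed based on the safety set".

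Other sections treat the cosmetic result differently:

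- Section 3.2 opens its list of secondary objectives with "Assessment and comparison between randomized arms of". Item 7 on that list is "cosmetic results (5 Point Scoring System, key secondary objective and subjective".
- Section 3.1 gives the endpoint a deciding role. If non-inferiority but not superiority is confirmed, "the cosmetic results (key secondary endpoint) need to be better in the preoperative radiotherapy arm" for the trial to change practice. Section 9.3.1 repeats this rule for the dichotomised scale (excellent/good against moderate or worse).
- That rule and the power statement for the cosmetic endpoint both stand in section 9.3.1, which is headed as the efficacy analysis. Section 9.2.1 says that the ITT set, analysed as randomised, "will be the primary population for efficacy endpoints".

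**The concern.** As-treated grouping is usual for toxicity. Here it also governs a superiority comparison on which the trial's recommendation may depend. If patients leave their allocated sequence for reasons linked to prognosis or to the surgery they need, the as-treated groups are no longer comparable. The cosmetic difference can then be biased even with no true effect.

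The protocol leaves a route for this. Under the synopsis (Randomization procedure), patients are randomised before the first assessment of response to NACT. The trial is open. Under section 6.3, local physicians decide further treatment after locoregional progression on NACT. An experimental-arm patient who then goes straight to surgery would be counted in the postoperative group.

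If net movers out of the experimental arm have worse cosmesis, the comparison favours that arm spuriously. If theirs is better, a true benefit is masked. Section 9.3.1 asks only that the result be better and sets no minimum difference for the practice-change rule.

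**Working it through.** **1. The protocol's own figure.** Section 9.3.1 claims over 90% power for a 15-point improvement at any control rate. With 913 per arm (section 9.4) and a two-sided 5% level, the normal approximation gives more than 0.999 at every control rate from 5% to 84%. Exact Fisher power also exceeds 0.999 at control rates of 20%, 42.5% and 70%. The claim reproduces, so the difficulty lies in the grouping and not in the power.

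**2. Effect of as-treated grouping with no true effect.** The protocol gives no regrouping rate, so every input except N and alpha is assumed:

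- *p* = 0.60 excellent/good in both randomised arms
- *fo* = share moving out of the experimental arm, *fi* = share moving into it
- *s* = success rate among movers
- N = 913 per arm, all assessed

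The as-treated rates are:

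- experimental: (p − fo·s + fi·s) / (1 − fo + fi)
- standard: (p + fo·s − fi·s) / (1 + fo − fi)

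Example with fo = 5%, fi = 0, s = 0.40:

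- experimental: (0.60 − 0.02)/0.95 = 0.6105
- standard: (0.60 + 0.02)/1.05 = 0.5905
- difference: 0.0201
- group sizes: about 867 and 959
- standard error: √[0.24 × (1/867 + 1/959)] = 0.0230
- significance threshold: 1.96 × 0.0230 = 0.0450
- chance of a significant result for the experimental arm: 1 − Φ((0.0450 − 0.0201)/0.0230), about 0.139

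| Out / in | Movers' rate | Spurious difference (points) | False win, experimental arm |
|---|---|---|---|
| 2% / 0% | 40% | +0.80 | 0.054 |
| 5% / 0% | 40% | +2.01 | 0.139 |
| 10% / 0% | 40% | +4.04 | 0.418 |
| 5% / 3% | 40% | +0.80 | 0.054 |
| 5% / 5% | 40% | 0 | 0.025 |
| 2% / 0% | 50% | +0.40 | 0.037 |
| 5% / 0% | 50% | +1.00 | 0.064 |
| 10% / 0% | 50% | +2.02 | 0.139 |

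The nominal value is 0.025 per side. Movers at 80% reverse the sign: 5% out gives −2.01 points and a 0.139 chance of a false result for the standard arm. A simulation of 40,000 trials per scenario with movers at 40% gave 0.055, 0.135 and 0.419 for 2%, 5% and 10% out. As-randomised grouping stayed between 0.023 and 0.027 per side throughout. With a base rate of 70% and movers at 50%, the figures are similar: 0.056, 0.152 and 0.466.

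**3. Cost of as-randomised grouping.** Non-receipt dilutes the effect. If 20% do not receive the allocated sequence, 15 points become 15 × 0.80 = 12 points.

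| Evaluable per arm | Power for 12 points, control rates 40–70% |
|---|---|
| 913 | 0.9993 to >0.9999 |
| 600 (assumed) | 0.987 to 0.998 |

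With half the sample evaluable (457 per arm, assumed), the minimum over all control rates is 0.954.

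**The case against.** The opposing case has four parts.

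- **The section 3.2 heading covers more than cosmesis.** It also covers quality of life, lymphoedema, plexopathy and toxicity, for which as-treated analysis is acceptable or common. Section 9.2.2 is a specific rule, while section 9.2.1 is general and mentions DFS in particular. This is fair: the heading alone does not settle the matter. But only the cosmetic result has a practice-change rule and a power statement in the efficacy section, and that sets it apart.
- **Little regrouping is likely.** Section 5.1 requires an indication for radiotherapy. Section 6.4.3 gives whole breast radiotherapy to all experimental-arm patients. Section 6.3 keeps the allocated sequence when NACT stops early for toxicity. Section 6.7 removes patients with distant metastasis or withdrawal before local therapy. The surgery-only group foreseeable from section 4.6 (cT1/T2 cN0 with mastectomy) would be in the standard arm, where the rule moves nobody. All this stands and makes the 10% scenario an upper illustration.
- **The false-win rates assume that all 913 per arm are assessed.** With 600 per arm, 5% net movement gives about 11% instead of 14%, and 2% gives about 4.7% instead of 5.4%. Significance at 913 per arm needs about 4.5 points, so a spurious win would usually fall well short of the 15 points that section 9.3.1 calls clinically relevant. This also stands, although 15 points is the planning effect and not a condition of the decision rule.
- **Missing cosmetic scores may be the larger threat.** Section 8.4 schedules scoring after 1, 3, 5, 7 and 9 years, and regrouping does nothing for missing scores. That is correct and remains a limitation.

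**Conclusion.** The point holds. Section 9.2.2 fixes an as-treated grouping for an endpoint whose objective is a comparison of randomised arms. That endpoint can decide whether the trial changes practice, and no as-randomised analysis of it is provided anywhere.

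The inconsistency is certain, but the size and direction of the bias are not. Under the assumptions above, it runs from nil (balanced movement) through 0.8 points at 2% net movement to 4.0 points at 10%, and it reverses if movers do better. It matters only if non-inferiority is shown without superiority. As-randomised grouping removes this source of bias, provided missing scores do not differ between arms. The protocol should be changed, but the point does not put the primary analysis in doubt.

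**What to change.** In section 9.2.2, take the cosmetic key secondary endpoint out of the safety set. State there, with one matching line in section 9.3.1, that it is analysed primarily as randomised, in all randomised patients with a cosmetic assessment. Name the analysis by treatment received as a sensitivity analysis, and note that differential missingness of scores remains a limitation. Toxicity can stay in the safety set.

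Make the change before outcome data are seen, since a grouping chosen afterwards would be open to challenge. No new data and no change in sample size are needed. The only statistical cost is the slight dilution quantified above.

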9.3 Methods of statistical analysis

9.3.1 Efficacy analysis

The primary endpoint of the trial is DFS. DFS as primary endpoint is defined as time from randomisation to any of the following events: local recurrence, regional recurrence, contralateral breast cancer, distant recurrence, invasive second cancer or death from any cause, whichever occurs first; patients without an event will be censored at the date of the last contact.

The primary hypothesis is that preoperative radiotherapy improves DFS compared to postoperative radiotherapy.

The primary efficacy analysis will follow the ITT (“treatment policy”) principle. DFS will be displayed by treatment group as Kaplan-Maier curves with 5 year and 8-year rates with the respective 95% confidence intervals and compared using the 2-sided stratified log-rank-test to the significance level of $\alpha=0.05$; all stratification factors for randomization will be used in the stratified test. Drop-out will be dealt with as independent right censoring. In addition, the

treatment effect will be estimated as a hazard ratio in a Cox proportional hazard regression model including treatment and stratification characteristics, the Wald p-value from the Cox regression will be the primary analysis to the significance level of $\alpha=0.05$. The hazard ratio will be reported with 95% confidence interval.

We will perform a hierarchical test, starting with non-inferiority as the first primary analysis (in both ITT and (as a sensitivity analysis) in per protocol sets). If this is significant in ITT set, then superiority as the second component of the main analysis will be tested [50].

The margin for the non-inferiority will be defined as 95% CI for HR <1.15 , which corresponds to the absolute difference of 3.6% in 10 years DFS rate (from 70% to 66.4%) or 2.2% absolute difference in 5 years DFS rate. This difference implies that the survival curve for DFS in the experimental arm will not run below that of the standard arm at most parts of the curve. Combined with the relatively narrow confidence limits, we expect that most clinicians would consider this result as clinically acceptable to recommend the experimental treatment, if the cosmetic results would be favourable.

Further explorative multivariate analysis, including other factors (e.g. grading, menopausal status, tumor size; the final list will be defined in the SAP) will be performed if deemed useful.

Regarding the primary endpoint the following predefined subgroups will be analysed in the similar way (stratified by the remaining stratification factors in case of a subgroup defined by a stratification factor): subgroups by biological subtype (HER2+ vs HER2-negative/HR-positive vs TNBC); ME, BET, Implant+/- Mesh. An interaction test will be performed for treatment against biological subtype. No adjustment for multiplicity is planned, the results should be considered as exploratory.

All secondary endpoints are defined in section 3.2.

The following secondary time-to-event endpoints will be analysed in a similar way (except for the non-inferiority): DDFS, OS, DSS.

LR (as a first site of recurrence) and RR (as a first site of recurrence) will be analysed using competing risk models: cumulative incidence function will be plotted and compared between treatment arms using (stratified) Gray's test; 5 year and 8-year cumulative incidence rates will be reported with the respective 95% CI; multivariate Fine-Gray model including treatment and stratification will be used to estimate hazard ratios with 95% CI.

Rates will be reported with 95% CI. Comparisons of the categorical data will be performed using Fisher's exact test (for pCR rates), or a trend test according to Cochran/Armitage (e.g. for cosmetic results), as suitable; further explorative multivariate analyses, including other relevant models (e.g. logistic regression) will be performed if deemed useful. Subgroups analyses in the same predefined subgroups as for the primary analysis will be performed if deemed useful.

If only non-inferiority but not superiority is confirmed, the cosmetic results (dichotomized as excellent/good vs moderate or worse, key secondary endpoint) must be better in the preoperative radiotherapy arm for the study to be able to change clinical practice. With the sample size of the study, the exact test of Fisher will have over 90% power to detect a clinically relevant improvement by 15% irrespective of the rate of excellent/good cosmetic results in the control arm.

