	
treatment effect will be additionally estimated as a hazard ratio in a proportional hazard's regression model with treatment and stratification characteristics.
 
The hazard ratio will be reported with 95% confidence intervals. Drop-out will be dealt with as independent right censoring.
 
We will perform a hierarchical test, starting with non-inferiority as the first primary analysis. If this is significant, then superiority as the second component of the main analysis will be tested.
 
The non-inferiority margin is defined as 95% CI for $HR < 1.15$ which corresponds to the absolute difference of 3.6% in 10 years DFS rate (from 70% to 66.4%) or 2.2% absolute difference in 5 years DFS rate.
 
Time to LR and time to RR will be analyzed using competing risk models.
 
Comparisons of the categorical data, e.g. response rates, dichotomized cosmetic results etc., will be performed using Fisher's exact test, or a trend test according to Cochran/Armitage for ordinal scales, as suitable.

Planned interim analyses	
While the pre-planned early safety assessment after n=100 patients is described in detail in section 4.6, no interim analyses of efficacy with early stopping option are planned. This is due to the fact that statistically significant differences in DFS and OS will first be measurable at a minimum of 5 years follow-up when the recruitment is completed, and an interim analysis would not allow for a reduction of patient numbers to be randomized.

Translational research (financial funding is applied separately)	
Extensive translational research programs based on certified longitudinal biobanking of blood plasma, serum and stool will be implemented to further refine molecular prognostic and predictive profiling using Liquid Biopsy approaches, and eventually identifying subgroups for treatment stratification.
 
The application for funding has been submitted. Once the German Cancer Aid has committed to the funding, the samples can be collected.

Estimated number of sites	In total approximately 40 study sites in Germany are planned to recruiting patients.
Study duration	
Start of preparation: Q3 2018
 
Start of recruitment: Q1 2024
 
Planned termination of recruitment: Q1 2028
 
Planned termination of follow-up: Q1 2034
 
Final study report: Q4 2034

ORGANISATION OF THE STUDY

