
benefit in DFS at 20 years for the preoperatively irradiated patients. The corresponding overall survival benefit was only 3%, which could be explained by the fact that the majority of patients in the database were treated in the last century, starting from 1972. Therefore, the same problems apply as described above. Brackstone et al. [7] published a matched pair analysis that compared a small cohort of high-risk breast cancer patients (n=108) receiving preoperative radiotherapy after NACT to postoperative radiotherapy. In this cohort, modern chemotherapy regimens and modern radiation techniques were used. At 4 years follow-up, an absolute advantage of 19% was observed for DFS and 14% for overall survival in favour of the preoperatively irradiated cohort.

In summary, there is sufficient evidence to postulate that preoperative radiotherapy after NACT could improve DFS compared to postoperative radiotherapy, but data from a randomized trial using modern systemic treatment and radiation techniques is missing.

Some investigators may argue that the observation of a pCR after preoperative radiotherapy after NACT could not have the same predictive value compared to a pCR after NACT alone, since a higher pCR rate is expected after additional radiotherapy. This could potentially be hazardous, since some patients, who would be candidates for postneoadjuvant chemotherapy or TD-M1 would not receive this treatment. However, the long term survival data (15 years) from a larger cohort of 315 patients treated with preoperative chemotherapy and radiotherapy at the University Hospital Duesseldorf [8] clearly indicates that pCR after preoperative radiotherapy and chemotherapy has the same impact on survival (no pCR 55% at 15 years, pCR 85% at 15 years) as typically observed in trials on NACT alone [9-11]. In addition, retrospective data have shown that higher pCR rates after additional radiotherapy after NACT compared to sole NACT can be expected especially in luminal B breast cancers, whereas a further increase of the already high pCR rates in Her2 positive and triple negative breast cancer will be less pronounced. The potential risk that less patients will receive postneoadjuvant treatment after preoperative radiotherapy is minimized in the present trial, since an axillary sentinel node biopsy is highly recommended before radiotherapy in the experimental arm and a biopsy of the residual breast lesion is recommended.

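### pCR and cosmetic results are compared with unstratified tests although randomisation is stratified; this costs efficiency, mainly for pCR, but does not make the tests invalid

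*Protocol*

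**What the plan says.** Section 9.1 describes the allocation: "Patients will be randomized to either the experimental arm or the standard of care arm in a 1:1 ratio, stratified by the following parameters". The first factor is "biological subtype: Strata: Her2-type (HER2/neu positive), HR + type (no HER2/neu overexpression), triple negative"; the others are cN status before chemotherapy and planned surgery (breast-conserving or mastectomy).

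Section 9.3.1 uses these factors for DFS, in a stratified log-rank test and a Cox model. DDFS, OS and DSS follow the same approach, and local and regional recurrence get a Gray's test (stratification in brackets) and a Fine-Gray model with the stratification factors.

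The categorical endpoints are handled differently. Section 9.3.1: "Comparisons of the categorical data will be performed using Fisher's exact test (for pCR rates), or a trend test according to Cochran/Armitage", the latter with cosmetic results as its example. Synopsis: "Comparisons of the categorical data, e.g. response rates, dichotomized cosmetic results etc., will be performed using Fisher's exact test". Neither place mentions strata. Adjusted modelling is optional and names no covariates: "further explorative multivariate analyses, including other relevant models (e.g. logistic regression) will be performed if deemed useful".

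The power statement for the key secondary cosmetic endpoint also rests on the unstratified test: "the exact test of Fisher will have over 90% power to detect a clinically relevant improvement by 15" per cent, whatever the control rate.

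Section 2.1 says that the gain in pCR is expected mainly in luminal B disease, "whereas a further increase of the already high pCR rates in Her2 positive and triple negative breast cancer will be less pronounced".

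**The concern.** When allocation is balanced within strata that predict the outcome, between-stratum variation largely drops out of the arm difference. An unstratified test still counts that variation as noise. Its standard error is too large, it rejects a true null hypothesis less often than its nominal level, and it has less power than a stratified test on the same data.

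The protocol applies this reasoning to its time-to-event endpoints but not to pCR or cosmesis. Cosmesis carries weight: under sections 3.1 and 9.3.1, if only non-inferiority of DFS is shown, the trial can change practice only if cosmetic results are better in the preoperative arm. What is at stake is precision, and power for effects smaller than those the protocol has in mind.

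**Working it through.** **1. The protocol's own power figure.** Inputs: 913 per arm and a 15-point gain (sections 9.4 and 9.3.1); two-sided 0.05, stated for DFS and assumed here. The least favourable pair is 0.425 against 0.575. For 90% power, n per arm = [1.960·√(2·0.5·0.5) + 1.2816·√(2·0.425·0.575)]² / 0.15² = 231.4, so 232, or 245 with continuity correction. At 913 per arm, simulated Fisher power is about 100% for control rates of 0.30 to 0.80. With only 250 per arm evaluable it is still 91% in the least favourable case. The stated figure holds.

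**2. Effect of ignoring the strata.** Let stratum k have weight w_k and rate p_k, with overall rate p. Then total variance = p(1−p), within-stratum variance = Σ w_k p_k(1−p_k), R = within/total, and the true level of a nominal 5% unstratified test ≈ 2·[1 − Φ(1.96/√R)]. The protocol gives no stratum rates, so all rates and weights below are assumptions. One factor is modelled per endpoint.

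Worked case, pCR in HER2+/HR+/triple negative at 50/15/45%, weights 30/40/30%:
- p = 0.150 + 0.060 + 0.135 = 0.345
- total variance = 0.345 × 0.655 = 0.2260
- within-stratum variance = 0.0750 + 0.0510 + 0.0743 = 0.2003
- R = 0.886, √R = 0.941, 1.96/0.941 = 2.082, true level = 0.037

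The same formula for all scenarios (cosmesis weights: 70% breast-conserving, 30% mastectomy):

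| Assumed rates | R | True level, before Fisher's discreteness |
|---|---|---|
| pCR 35/20/35% | 0.974 | 0.047 |
| pCR 50/15/45% | 0.886 | 0.037 |
| pCR 65/10/50% | 0.757 | 0.024 |
| Cosmesis 70/60% | 0.990 | 0.049 |
| Cosmesis 75/55% | 0.961 | 0.046 |
| Cosmesis 80/40% | 0.846 | 0.033 |

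**3. Simulation at 913 per arm, balanced within strata.** CMH is the Cochran-Mantel-Haenszel test. Power is at a common log odds ratio of 0.3.

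| Scenario | Type I error, Fisher / CMH | Power %, Fisher / unstratified chi-square / CMH |
|---|---|---|
| pCR 35/20/35% | 0.041 / 0.049 | 81.4 / 82.8 / 83.6 |
| pCR 50/15/45% | 0.033 / 0.049 | 77.7 / 79.3 / 83.0 |
| pCR 65/10/50% | 0.024 / 0.051 | 65.3 / 67.4 / 78.0 |
| Cosmesis 70/60% | 0.044 / 0.051 | 81.6 / 83.1 / 83.2 |
| Cosmesis 75/55% | 0.036 / 0.044 | 78.1 / 79.5 / 80.5 |
| Cosmesis 80/40% | 0.030 / 0.050 | 68.9 / 71.0 / 76.3 |

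The CMH levels of 0.044 to 0.051 around a nominal 0.05 indicate the simulation error.

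Fisher falls short of CMH by 1.6 points (83.22 − 81.59, cosmesis 70/60%) to 12.8 points (78.04 − 65.29, pCR 65/10/50%). Part of this is Fisher's discreteness. Comparing chi-square with CMH isolates the strata: 0.15 points (83.22 − 83.07) to 10.7 points (78.04 − 67.37).

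**4. At the effects the protocol names.** For a 15-point cosmetic gain with breast-conserving/mastectomy control rates of 70/30%, both tests have about 100% power at 913 per arm; at 250 per arm, Fisher has 95% and CMH 98%. For pCR, section 4.6 expects about 20% more complete remissions. Its own arithmetic, 20% × (1 − 60%) = 8%, treats these as percentage points. The largest standard error is √(2 × 0.25/913) = 0.0234, so z ≈ 0.20/0.0234 = 8.5. Half that gain gives z ≈ 4.3 and power of about 99%.

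**The case against.** The strongest reply is that no planned inference is wrong. The tests are conservative, so a significant result stands. Step 4 shows that at the protocol's own cosmetic and pCR effects both tests would almost always agree. This stands, and it limits the point to efficiency. A reader might infer from the role of cosmesis in the practice-change rule that the rule is underpowered; the documents do not support that.

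Four further limits stand:
- Section 9.3.1 promises 95% CIs for rates only and specifies none for an arm difference in these endpoints. One cannot say that a planned interval is too wide, and stratified allocation does not widen a single-arm interval.
- A reader might infer that all three factors predict both outcomes. The text supports subtype for pCR. For cosmesis, section 2.1 says that the expected advantage varies with the surgical procedure. That describes a varying treatment effect and does not establish different baseline rates. Nothing links subtype or cN status to cosmesis.
- The size rests on assumed rates, and its lower end is negligible.
- Cosmesis is analysed as treated in the safety set (section 9.2.2), so balance within strata is only approximate there.

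It can also be said that tests are to be used as suitable and that section 9.6 leaves further detail to the SAP. This carries less weight: the protocol names the tests in two places and bases a power statement on one of them, so this is a stated choice and not an omission.

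**Conclusion.** The point holds as a loss of efficiency. The protocol stratifies randomisation, uses the strata for time-to-event endpoints, and names unstratified tests for pCR and cosmesis. In every scenario examined, Fisher's test ran below its nominal level (0.024 to 0.044) and had less power than the stratified test, by 1.6 to 12.8 points at a log odds ratio of 0.3. Those figures depend on assumed stratum rates and weights.

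The direction is well supported for pCR, where the protocol itself reports differences by subtype. For cosmesis it is conditional on a difference in excellent/good rates by planned surgery that the protocol does not give. With weakly prognostic strata the loss from ignoring them is negligible, and most of the remaining shortfall is Fisher's discreteness.

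A reader might conclude that the tests are invalid because their true level is not 5%. That is not supported: the departure is on the conservative side. The claim of over 90% power for 15 cosmetic points reproduces with a wide margin.

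**What to change.** In section 9.3.1 and the synopsis:
- Make a Cochran-Mantel-Haenszel test stratified by the randomisation factors the main comparison for pCR and for dichotomised cosmesis, with a stratified risk difference and 95% CI.
- Use a stratified (extended Mantel-Haenszel) trend test for the ordinal cosmetic score.
- Report pCR by subtype and cosmesis by planned surgery alongside, because the protocol expects the effect to differ and one pooled estimate would hide this.
- Keep Fisher's test as a sensitivity analysis.

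The baseline cosmetic score could be added as a covariate, but only once its timing is reconciled. Section 8.4 places it before whole-breast radiotherapy, which in the standard arm is after surgery. Tables 3 and 4 place it before local therapy in both arms.

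The cost is wording only, with no new data or patients. The 12 strata average 1826/12 ≈ 152 patients, but cells will be uneven: with 25 to 30% planned mastectomies (assumed), the six mastectomy strata average 1826 × 0.25/6 ≈ 76 to 1826 × 0.30/6 ≈ 91, before losses. The Cochran-Mantel-Haenszel test tolerates this and does not need exact balance.
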